Helping patients find effective strategies for dealing with chemotherapy is an important task for nurses. Complementary interventions to pharmacological treatment aim to reduce suffering at different stages of treatment.

Based on these scenario, we seek therefore produce and study an image database and validate them scientifically, aiming initially the care settings, in order to produce well-being for patients undergoing chemotherapy, as well as deepen our knowledge of man-nature connection, from the perspective of care, self-care and preservation.

2. Objectives

Verify the therapeutic potential of the validated images in the reduction of negative mood states and increase of positive states of patients undergoing the chemotherapy session.

Verify the therapeutic potential of the validated images in the treatmentrelated symptoms during the chemotherapy session.

Verify if the rate of connection with nature influences the impact in the study outcomes.

3. Design and methods

The previously validated e-Natureza image bank consists of licensed images by nature photographers who volunteered to contribute to the development of the project. They are photos with predominance of flowers, colorful birds, white birds, landscapes, photos with predominance of trees, predominating the element water, with predominance of sky, photos related to the sea, totaling 480 images.

The final image bank consists of the validated images that reached the low alert and high valence scores, that is, photos that were concentrated in the lower right quadrant of the figure below, with a view to promoting well-being and tranquility.

[figure not shown]

Figure 1 - Distribution of 360 images of International Affective Picture System (IAPS).

The randomized clinical trial will be conducted at the same institution, Albert Einstein Hospital, that the nature images were validated. The date collection of the clinical trial will be done in a period of 12 months, together with a convenience sample of patients, of both sexes, who is over 18 (eighteen), with clinical conditions and communication systems preserved, in other words, lucid, that allows the participation in the study and who are undergoing the first session of the chemotherapy treatment (most patients in the first session, have an altered emotional state, be it for fear, anxiety) independently of the type of oncological disease.

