The patients, after understood and signed the Informed Consent Form will respond to a questionnaire with sociodemographic and clinics variables (gender, age, marital status, schooling, profession, relationship with nature, diagnosis, treatment time, protocol type) for characterization of the sample (Appendix I).

The patients will be allocated randomly into two groups: 1) control and 2) intervention group through Randomizer® software.

After thirty minutes of the start of the chemotherapy session, the patient you will receive a notebook (specific to the study and blocked for other functions) that he can watch a presentation of nature images. It will be four videos with fifteen minutes each one.

At the beginning and at the end of the chemotherapy session, each patient will make an assessment of the positive and negative affects and the physical and psychological symptoms related to that chemotherapy session.

According to Paschoal and Tamayo (2008), measures of affection reflect how much the person feels enthusiastic, alert and active. The negative affect reflects how much the person feels displeasure and distress. According to these authors, one of the main affective measures used in study of general well-being is the Positive Affect/Negative Affect Scale, which through 20 words that describe feelings that should be answered on a five-point scale: "very little or nothing", "a little", " moderately", " too much", and "excessively", allowing use as a measure of state or trace. In Brazil, PANAS (Annex I) was adapted for the adult population by Giacomoni and Hutz and for adolescents by Segabinaz et al (2013), already validated elderly people in a virtual environment.

The evaluation of symptoms during the chemotherapy session also will be evaluated by - Edmonton Symptom Assessment Scale – ESASBr - (Annex II).

The Edmonton Symptom Assessment System (ESAS) is a widely used multi-symptom assessment tool, developed for the first time in 1991 by Bruera et al. to audit the symptoms of patients receiving palliative care. The ESAS is a viable, valid and reliable multi-symptom assessment tool for use in Brazil (Paiva, et al, 2015).

The participants will also respond pre intervention to the Nature Connection Scale and Nature Relatedness Scale (Annex III and IV) because it is a variable that can interfere in the study's outcomes of interest.

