The control group will undergo the same evaluations as the intervention group and at the same time interval during the chemotherapy session.

All evaluations will be performed in only one chemotherapy session.

4. Statistical analysis plan

Descriptive statistics will be applied to sociodemographic and clinical data of the study, with calculation of means and standard deviation.

By means of inferential statistics, a comparison will be made between the states subsequently presented by the patients in the clinical trial, using SPSS statistical software. For analysis correlation will be used the Spearman and Pearson tests; for averages comparison if the sample is normal, the paired t-test will be used; for nonparametric sample the Wilcoxon test, and the Fisher and chi-square tests for compare proportions. The tests will be considered significant when p <0.05.

5. History of changes

- Research Project- Version 1- submitted to Research Ethics Committee of the Hospital Israelita Albert Einstein in December 23, 2016;
- Informed Consent Form Patient- Version 1- submitted to Research Ethics Committee of the Hospital Israelita Albert Einstein in December 23, 2016;
- Documentation approved by the Research Ethics Committee of the Hospital Israelita Albert Einstein in the first version at a meeting held in 01/31/2017.
- Documentation disapproved by ClinicalTrials.gov in the first version in 03/16/2017;
- Documentation disapproved by ClinicalTrials.gov in the second version in 03/28/2018;
- Documentation disapproved by ClinicalTrials.gov in the third version in 04/16/2018.

6. Research ethics committee original report translated to English*

*The original one is in Portuguese

HOSPITAL ISRAELITA ALBERT EINSTEIN- SP

CONSUBSTANTIATED TECHNICAL ADVICE OF RESEARCH ETHICS COMMITTEE

RESEARCH PROJECT DATA

Research title: e-Natureza: Affective Validation of Nature Images as a Complementary Resource for Promoting Well-being in Hospital Environment

Researcher: [name]

Thematic area:

Version: 1

CAAE: 64096816.9.0000.0071.

Proponent institution: Hospital Israelita Albert Einstein-SP

Principal Sponsor: Hospital Israelita Albert Einstein-SP

TECHNICAL ADVICE DATA

Technical advice number: 1.906.315

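### Section 4 lets an unspecified normality check choose between a paired t-test and a Wilcoxon test, judges by p<0.05, and plans no between-arm estimate or interval for PANAS or ESAS

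*Combined protocol and SAP*

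**What the plan says.** Section 3 (Design and methods) describes a two-arm randomised trial: "The patients will be allocated randomly into two groups: 1) control and 2) intervention group". Affect and symptoms are measured twice within one session: "At the beginning and at the end of the chemotherapy session, each patient will make an assessment of the positive and negative affects", with ESAS alongside. The control group has the same assessments at the same interval.

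Section 4 (Statistical analysis plan) states the inferential aim loosely: "a comparison will be made between the states subsequently presented by the patients in the clinical trial". For means it gives a conditional rule: "for averages comparison if the sample is normal, the paired t-test will be used; for nonparametric sample the Wilcoxon test". It closes with the criterion: "The tests will be considered significant when p <0.05".

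The only summary statistics it names are tied to background data: "Descriptive statistics will be applied to sociodemographic and clinical data of the study, with calculation of means and standard deviation". It names no effect measure or confidence interval for PANAS or ESAS. On recruitment, Section 3 says that data collection "will be done in a period of 12 months, together with a convenience sample of patients". Sections 3 and 4 give no number of patients, target difference or power.

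**The concern.** There are three problems in one short rule.

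- **The test is chosen on outcome data by an undefined condition.** The plan names no normality test, threshold or variable (raw score, change or residual). Two analysts could follow it faithfully and run different tests on the same data.
- **The branches answer different questions.** A t-test concerns a mean; a Wilcoxon test concerns a rank-based shift. The objectives cover positive affect, negative affect and symptoms, so the three could be tested on different scales. With only a p-value planned, none of them would come with a size of effect, although Section 2 sets out to verify therapeutic potential.
- **The named t-test is paired.** It asks whether patients in one arm changed over the session. Section 3 says that patients at a first session are often fearful or anxious, so scores may move by the end of it in both arms. A significant change within the intervention arm would not show that the images caused it.

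A non-significant result is also hard to read without an interval, because p>=0.05 does not separate a small effect from an imprecise estimate.

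**Working it through.** The plan gives no sample size, SD, target difference or power, so it has no figure to reproduce. The inputs from the documents are the branching rule and the 0.05 threshold (Section 4), and two randomised arms measured at the start and end of one session (Section 3). Everything else below is an assumption: two-sided tests, 1:1 allocation, Shapiro-Wilk at 0.05 on the paired changes as the normality check, signed-rank as the Wilcoxon test, and the distributional shapes.

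**1. What each branch tests.** Let D be a patient's end score minus start score.
- Paired t-test: mean of D = 0.
- Signed-rank test: D symmetric about 0, so that the median of pairwise averages of D (the pseudomedian) is 0.

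The two agree when D is symmetric and can differ when it is skewed. Take D = E - 1 with E a unit exponential. The mean is 1 - 1 = 0. The median is ln 2 - 1 = -0.31. The average of two independent copies of E has median 1.678/2 = 0.839, so the pseudomedian is 0.839 - 1 = -0.16. The t-test null is true and the signed-rank null is false.

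**2. Simulation of the switch** (2,000 runs per cell, paired changes, no mean change in any row):

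| Shape of D | n | Sent to Wilcoxon | t-test rejects | Switch rejects |
|---|---|---|---|---|
| Normal | 20 | 5.3% | 4.7% | 4.7% |
| Normal | 30 | 5.7% | 4.3% | 4.4% |
| Normal | 60 | 4.6% | 4.8% | 4.9% |
| Difference of two skewed 0-10 items | 20 | 84% | 5.5% | 5.2% |
| Difference of two skewed 0-10 items | 30 | 98% | 5.4% | 5.5% |
| Difference of two skewed 0-10 items | 60 | 100% | 4.7% | 4.3% |
| Centred exponential | 20 | 82% | 8.0% | 12.7% |
| Centred exponential | 30 | 96% | 6.5% | 14.8% |
| Centred exponential | 60 | 100% | 7.0% | 27.9% |

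A separate run of the centred exponential gave 13%, 17% and 26% for the switch, and 6-9% for the t-test. The Monte Carlo standard error at the largest value is sqrt(0.279 x 0.721 / 2000) = 0.010, so the last row is best read as a little over one quarter.

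Normal changes almost always go to the t-test, and 0-10 items of the assumed shape almost always go to Wilcoxon. Mixed tests across scores are therefore a realistic result. In the skewed case the rejection rate rises with n because the switch has moved to a different null hypothesis, one that is false.

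**3. Which contrast.** Write the mean change in the control arm as s (the session) and in the intervention arm as s + e (the session plus the images). A paired test in the intervention arm tests s + e = 0. The randomised comparison is (s + e) - s = e. With e = 0 and s not zero, the paired test will still tend to reject as n grows.

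**4. What a bare null would leave open.** For two arms of n patients, the unadjusted 95% CI half-width is 1.96 x sqrt(2/n) SD. Power is for a true difference of 0.5 SD at two-sided 0.05.

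| n per arm (assumed) | Half-width | Power |
|---|---|---|
| 20 | 0.62 SD | 35% |
| 30 | 0.51 SD | 49% |
| 60 | 0.36 SD | 78% |
| 100 | 0.28 SD | 94% |

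At 30 per arm a non-significant result is compatible with differences of about half an SD either side of the estimate.

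**The case against.** The strongest defence is that choosing a t-test or a Wilcoxon test by shape is common practice and usually does little harm. The simulation partly bears this out: with normal or symmetric changes the switch rejected in 4.3-5.5% of samples. A reader might infer from the skewed case that the rule inflates Type I error generally. It does not. The excess appears when changes are skewed with mean zero, and even there the signed-rank test is correctly rejecting its own null. The fault is that the plan does not say which null it means.

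Other stronger readings also go beyond the text:
- *Normality is checked on the wrong variable.* The plan names no variable, and the sample could mean the paired differences. The supportable criticism is that it is unspecified. For the same reason no single rate of mixed tests can be given: it depends on whether end scores or changes are checked.
- *Bounded integer scores make the t-test invalid.* No t-test needs exact normality.
- *The plan intends different effect measures for different scores.* It names none. Different scales are a consequence of the rule.
- *Intervals are excluded and a null could not be interpreted.* The interval is simply not planned. One reported later would partly repair a null result, though not the data-driven choice of test.
- *The trial has no sample size.* That holds only for the readable text, since some of the document was not available for review.

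Finally, the opening sentence of the inferential plan is loose enough to cover a between-arm comparison, and Wilcoxon could mean the rank-sum test. That reading does not rescue the rule. The t-test is explicitly paired, so the normality result would then decide whether the analysis is within or between arms.

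**Conclusion.** The concern holds as worded in the heading. Section 4 leaves the choice of test to an undefined look at the outcome data, offers two tests of different quantities, states only a p-value criterion for the outcomes, and names a paired test that does not address the randomised question.

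The effect on error rates is conditional: negligible for normal or symmetric changes, and about 13% rejection at n=20 rising to about 26% at n=60 for mean-zero changes with an assumed centred exponential shape, against 6-9% for the t-test. These figures rest on Shapiro-Wilk at 0.05 and signed-rank, neither of which the plan specifies. The precision figures rest on assumed arm sizes. The missing between-arm contrast needs no such assumptions; it follows from setting Section 3 beside Section 4, and it is the more serious part. The change is inexpensive and should be made before the outcome data are examined.

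**What to change.** In Section 4, delete the normality condition and replace the sentence on comparing means with one rule per score:

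- **Main analysis:** the between-arm difference in mean end-of-session score, adjusted for the start-of-session score already collected, reported with a 95% CI whatever the distribution looks like. Robust standard errors are one acceptable choice.
- **Sensitivity analysis:** a rank-based between-arm test, named in advance and labelled as such.
- **Reading of results:** conclusions rest on the estimate and its interval; p>=0.05 alone is not reported as no effect.

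The ESAS score or scores must be listed by name, because neither Section 3 nor Annex II defines a total.

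This needs no new data, visits or patients. It is more than an edit of wording, because it replaces a within-arm test by a between-arm contrast, and the text should say so. The statistical cost is slightly lower efficiency than ranks for a heavily skewed score.

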Project apresentation: In recent decades there has been a growing interest of researchers in understanding how the adoption of natural elements of daily life, including in hospital institutions, can characterize restorative environments and reflect in better health conditions for patients. Contact with nature can be done through photographs. However, there is no database of validated nature for clinical use (only for restricted use in research). This study aims to validate images of nature and verify its therapeutic potential in the care of cancer patients undergoing chemotherapy. Therefore, the research is divided into two phases. First we will build a web tool that allows the validation of nature photographs in accordance with international validation method. This phase will be conducted with students and health professionals as well as individuals from

the general population. The validated photographs will compose a database of images of which low activity and positive valence images will be used in the randomized clinical trial with patients on chemotherapy treatment. Anchored with assumptions from the theory of biophilia, from Florence Nightingale's environmental theory, our hypothesis of study is that this intervention promotes subjective well-being and favors more positive moods, in addition to reducing symptoms.

Research Objectives:

Contribute to the validation of images of nature for clinical use in health institutions

Specific:

1-Develop a tool that allows the application, in a web environment, of the affective classification of images of nature, according to the Self-Assessment Manikin method (SAM).

2-Validate the images of nature with students and health professionals and individuals of the general population.

3-Compare the scores obtained with similar photos that compose the IAPS image bank.

4-Verify if the factor related to nature and kinship with nature influence the affective validation of images.

5-Create an audiovisual nature image resource (e-nature) for clinical use in patients undergoing chemotherapy treatment.

6-Verify the therapeutic potential of the validated images in the reduction of negative mood states and increase of positive states of patients undergoing chemotherapy.

7-Verify the therapeutic potential of validated images in the reduction of treatment-related symptoms during the chemotherapy session.

8-Know the patient's perception about the intervention based on nature.

Assessment of risks and benefits:

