Annex II

Edmonton Symptom Assessment Scale – ESASBr

This is a symptom assessment scale. You will respond to 10 items with responses ranging from 0 (minimum intensity) to 10 (maximum intensity). Please circle the number that best describes your symptoms AT THIS TIME.

No pain	0	1	2	3	4	5	6	7	8	9	10	Worst possible pain
Not tired	0	1	2	3	4	5	6	7	8	9	10	Worst possible tiredness
Not nauseated	0	1	2	3	4	5	6	7	8	9	10	Worst possible nausea
Not depressed	0	1	2	3	4	5	6	7	8	9	10	Worst possible depression
Not anxious	0	1	2	3	4	5	6	7	8	9	10	Worst possible anxiety
Not drowsy	0	1	2	3	4	5	6	7	8	9	10	Worst possible drowsiness
Best appetite	0	1	2	3	4	5	6	7	8	9	10	Worst possible appetite
Best feeling of wellbeing	0	1	2	3	4	5	6	7	8	9	10	Worst possible feeling of wellbeing
No shortness of breath	0	1	2	3	4	5	6	7	8	9	10	Worst possible shortness of breath

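### No primary outcome is named and every test uses an unadjusted p<0.05: if any one of three scores may carry a benefit claim, the chance of a false-positive result is an illustrative 8–14% (4–7% in favour of the images), against 5% (2.5%) for one named test

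*Combined protocol and SAP*

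**What the plan says.** Section 2 (Objectives) sets a mood aim with two targets, "in the reduction of negative mood states and increase of positive states of patients undergoing the chemotherapy session", and a separate symptom aim, "Verify the therapeutic potential of the validated images in the treatmentrelated symptoms during the chemotherapy session". A third objective asks whether connection with nature influences the effect on the outcomes. None is ranked above another.

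Section 3 (Design and methods) has the outcomes measured at the start and end of a single session: "each patient will make an assessment of the positive and negative affects and the physical and psychological symptoms related to that chemotherapy session". The instruments are the PANAS (Annex I) and the ESAS (Annex II).

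Section 4 (Statistical analysis plan) applies one threshold throughout: "The tests will be considered significant when p <0.05". For means it says "for averages comparison if the sample is normal, the paired t-test will be used", with the Wilcoxon test as the nonparametric alternative.

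The project presentation in the ethics committee report (section 6) states the hypothesis that "this intervention promotes subjective well-being and favors more positive moods, in addition to reducing symptoms". It does not say how many of these must be shown.

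Part of the ethics committee report was not available for this review. Sections 2 to 4, where a primary outcome or multiplicity rule would normally stand, were.

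**The concern.** A 5% threshold holds the error at 5% for one test fixed in advance. Here at least three scores are candidates for the main conclusion, and the plan does not say which decides the trial or how many must succeed. If one significant score is enough, the chance that some score crosses the line by luck is higher than 5%.

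The lack of a ranking also allows the headline outcome to be chosen after seeing which score moved. A reader of the results could not then tell a planned finding from a selected one, and this cannot be repaired as credibly once arm results are known.

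**Working it through.** The plan gives no power, sample size or familywise error rate, so it has no figure of its own to reproduce.

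**Inputs**
- Threshold: 0.05 per test (section 4). Sidedness is not stated; two-sided is assumed, so 0.025 in each direction and a critical value c = 1.96.
- Number of scores: k = 3, namely PANAS positive, PANAS negative and one ESAS total (sections 2 and 3). The use of an ESAS total is an assumption, because the plan does not define the ESAS score.
- Test: a valid between-arm comparison of each score. This is also an assumption, since section 4 names only paired tests for means.
- Correlation ρ between test statistics, with scores signed so that benefit is positive: not given. Values of 0, 0.5, 0.7 and 0.9, equal for all pairs, are assumed.
- No true effect on any score, and any one significant score may be reported as benefit.

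**Independent scores (ρ = 0)**
- At least one significant: 1 − (1 − 0.05)³ = 1 − 0.8574 = 0.1426.
- At least one significant in favour of the images: 1 − (1 − 0.025)³ = 1 − 0.9269 = 0.0731.

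**Correlated scores**

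With φ and Φ the standard normal density and distribution function, a = (c − √ρ·u)/√(1 − ρ) and b = (−c − √ρ·u)/√(1 − ρ):
- At least one significant: 1 − ∫ φ(u)·[Φ(a) − Φ(b)]³ du.
- At least one in favour: 1 − ∫ φ(u)·[Φ(a)]³ du.

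| ρ | 0 | 0.5 | 0.7 | 0.9 | One named test |
|---|---|---|---|---|---|
| Any of three significant | 14.3% | 12.5% | 10.9% | 8.4% | 5% |
| Any of three, in favour | 7.3% | 6.3% | 5.5% | 4.2% | 2.5% |

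Whatever the correlation, the first row cannot exceed 3 × 5% = 15%, nor the second 3 × 2.5% = 7.5%.

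**Mood objective alone**
- Either PANAS score suffices (k = 2, same formula): 9.8%, 9.1%, 8.4% and 7.0% at the four correlations.
- Both PANAS scores required: 0.2%, 0.9%, 1.7% and 3.0% when neither score is affected. This is not the worst case. If one score truly moves, the chance of wrongly claiming both rises towards 5%, so the statement that holds is at most 5%.

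**Holm on the two PANAS scores**
- Familywise error: 4.9%, 4.7%, 4.3% and 3.6% at the four correlations.
- Power: a comparison with 80% power at 0.05 has a standardised effect of 1.960 + 0.842 = 2.802. At the first Holm step (0.05/2, critical value 2.241) its power is Φ(2.802 − 2.241) = Φ(0.561) ≈ 0.71.
- Sample size ratio to restore 80% at that step: (2.241 + 0.842)²/2.802² = 1.21.

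**The case against.** The strongest reply is that mood and symptoms are separate objectives. If each claim is confined to its own objective, a symptom claim tested once on an ESAS total carries 5%. If the mood objective needs both a fall in negative affect and a rise in positive affect, as its wording can be read, the mood claim carries at most 5%. On that reading nothing exceeds 5% per objective. This stands as a possible reading, but the plan does not adopt it. The hypothesis in the ethics report names mood before symptoms, but that order does not make mood primary.

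A second reply is that the figures do not measure this plan. The correlations, the sidedness, the between-arm test and the any-one-significant rule are all supplied from outside it. This is correct, and it is why the figures are given as an illustration with a range. The missing between-arm test is a separate defect; naming one would not supply a primary outcome.

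Two stronger readings are tempting and are not supported:
- A reader might infer from Annex II, which says "You will respond to 10 items with responses ranging from 0 (minimum intensity) to 10 (maximum intensity", that each symptom will be tested singly and that the error is far higher. The plan neither states nor excludes item-level testing, so no such rate can be attributed to it.
- A reader might infer that the investigators intend to report whichever score is significant. Nothing says so; the plan only fails to rule it out.

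**Conclusion.** The concern holds in a conditional form. The readable plan names no primary outcome, order of testing or multiplicity rule, and applies p<0.05 to every test. Confidence in that omission is high.

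If any one of the three scores may be reported as benefit, the chance of at least one false-positive result is about 8–14%, and 4–7% in favour of the images. The matching comparators are 5% and 2.5%; the in-favour range should not be read against 5%. The size rests on the assumptions listed above and is not the plan's measured error rate. Tests for the nature-connection objective are not counted.

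This should be corrected. The inflation is moderate and depends on a rule the plan leaves open, but the ambiguity itself weakens any positive result.

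**What to change.** Before arm results are seen, amend section 4 as follows.

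1. Choose one of:
   - **Option A.** Name one PANAS score at end of session as the primary outcome at two-sided 0.05. Which score is for the investigators to decide.
   - **Option B.** Make both PANAS scores co-primary with Holm.
2. Under either option, compare the arms with a between-arm analysis adjusted for the baseline score, which is already collected.
3. Define the ESAS analysis as one total, or treat its items as descriptive.
4. Make all other scores secondary. Either Holm-adjust them and test them only after the primary succeeds (both PANAS scores under option B), or report estimates with 95% confidence intervals and no significance claim.
5. Label the nature-connection analysis exploratory.

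The documents do not say whether analysis has begun; the last dated entry in section 5 is 04/16/2018. If arm results have already been seen, apply Holm across all measured efficacy scores, report all of them, and label the choice post hoc. The family must be all measured scores, because limiting it to reported scores would leave selective reporting open.

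**Cost.** The change is to SAP wording and needs no new data. Some nominal p<0.05 results could no longer be claimed, including, under option A, an effect confined to the PANAS score not chosen. Under option B, a comparison with an illustrative 80% power at 0.05 has about 71% at the first Holm step, and restoring 80% there would take about 21% more patients. The 80% is only a reference point, since the readable text states no power or sample size.
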